8.3. Dose Modification and Study Treatment Discontinuation Rules

8.3.1. Dose Modification

Dose modification of REGN9933 for an individual participant is not allowed.

Sites should follow the enoxaparin and apixaban dosing schedule outlined in Section 8.1. However, enoxaparin and apixaban may be temporarily interrupted or the dose reduced due to medical need, as determined by the investigator.

The criteria for permanent discontinuation of enoxaparin and apixaban are described in Section 8.3.2.2 and Section 8.3.2.3, respectively.

8.3.2. Study Intervention Discontinuation

Participants who permanently discontinue from study intervention (REGN9933, enoxaparin, or apixaban) should be encouraged to remain in the study. Those who agree and do not withdraw from the study will be asked to return to the clinic for all remaining study visits per the visit schedule.

Participants who permanently discontinue from study intervention and who opt to withdraw from the study will be asked to complete study assessments, per Section 9.1.2.

8.3.2.1. REGN9933 Discontinuation

As this is a single dose study of REGN9933, discontinuation of REGN9933 is not applicable. Refer to Section 8.4 for the Management of Acute Reactions including interruption and termination of REGN9933 IV infusion.

8.3.2.2. Enoxaparin Discontinuation

Enoxaparin should be discontinued:

- if there is clinical suspicion of HIT
- if there is active clinically significant bleeding

Further management of HIT, the bleeding event, and VTE prophylaxis and is left to the discretion of the investigator.

8.3.2.3. Apixaban Discontinuation

Apixaban should be discontinued:

- if there is active clinically significant bleeding

Further management of the bleeding event and VTE prophylaxis is left to the discretion of the investigator.

8.4. Management of Acute Reactions

8.4.1. Acute Intravenous Infusion Reactions

Emergency equipment and medication for the treatment of infusion reactions must be available for immediate use. All infusion reactions must be reported as AEs (as defined in Section 10.2.4) and graded using the grading scales as instructed in Section 10.2.5.

8.4.1.1. Interruption of the Intravenous Infusion

The infusion should be interrupted if any of the following AEs are observed:

- Sustained/severe cough
- rigors/chills
- rash, pruritus (itching)
- urticaria (hives, welts, wheals)
- diaphoresis (sweating)
- hypotension
- dyspnea (shortness of breath)
- vomiting
- flushing

The reaction(s) should be treated symptomatically, and the infusion may be restarted at 50% of the original rate.

If investigators feel there is a medical need for treatment or discontinuation of the infusion other than described above, they should use clinical judgment to provide the appropriate response according to typical clinical practice.

8.4.1.2. Termination of the Intravenous Infusion

The infusion should be terminated and NOT restarted if any of the following AEs occur:

- Anaphylaxis*
- laryngeal/pharyngeal edema
- severe bronchospasm
- chest pain
- seizure
- severe hypotension
- other neurological symptoms (confusion, loss of consciousness, paresthesia, paralysis, etc)
- any other symptom or sign that, in the opinion of the investigator, warrants termination of the IV infusion

*Consider anaphylaxis if the following is observed (Sampson, 2006): acute onset of an illness (minutes to several hours) with involvement of the skin, mucosal tissue, or both (eg, generalized hives, pruritus or flushing, swollen lips-tongue-uvula) AND AT LEAST ONE OF THE FOLLOWING

- Respiratory compromise (eg, dyspnea, wheeze-bronchospasm, stridor, reduced peak expiratory flow, hypoxemia)
- Reduced blood pressure or associated symptoms of end-organ dysfunction (eg, hypotonia [collapse], syncope, incontinence)

8.4.2. Acute Injection Reactions

8.4.2.1. Systemic Injection Reactions

Emergency equipment and medication for the treatment of systemic reactions must be available for immediate use. All injection reactions must be reported as AEs (as defined in Section 10.2.1) and graded using the grading scales as instructed in Section 10.2.5.

Acute systemic reactions following injection of study intervention (SC) should be treated using clinical judgment to determine the appropriate response according to typical clinical practice.

8.4.2.2. Local Injection Site Reactions

Local injection site reactions must be reported as AEs and graded according to Section 10.2.5.

8.5. Method of Treatment Assignment

Participants will be randomized after surgery to one of 3 treatment arms—REGN9933, enoxaparin, apixaban—in a ratio of 1:1:1, according to a central randomization scheme provided by an interactive voice response system (IVRS)/interactive web response system (IWRS) to the designated study pharmacist (or qualified designee). Approximately 120 participants will be enrolled in each arm, for a total of up to approximately 360 participants in the study.

Participants will be stratified based on study site and age (<70 vs ≥70 years of age).

8.6. Blinding/Masking

This is a phase 2 multicenter, multinational, randomized, open label, active-control study of a single dose of IV REGN9933 for prevention of VTE in participants undergoing an elective unilateral TKA.

Treatment is administered in an open-label manner because enoxaparin is packaged in pre-filled syringes, making blinding operationally challenging. To mitigate bias in outcome assessment, adjudication of outcomes related to VTE, and bleeding will be performed by a centralized AC that is blinded to treatment assignment (Section 6.3.3).

8.7. Treatment Logistics and Accountability

8.7.1. Packaging, Labeling, and Storage

A medication numbering system will be used to label investigational study drug. Lists linking medication numbers with product lot numbers will be maintained by the groups (or companies) responsible for study drug packaging.

Open-label study drug will display the product lot number on the label.

REGN9933 study drug should be stored at the site at a temperature of 2°C to 8°C; storage instructions will be provided in the pharmacy manual.

Enoxaparin and Apixaban should be stored at the site as follows: Do not store above 25°C (77° F); storage instructions will be provided in the pharmacy manual.

8.7.2. Supply and Disposition of Treatment

All study drug will be shipped at a temperature provided in the pharmacy manual to the investigator or designee at regular intervals or as needed during the study.

At specified time points during the study (eg, interim site monitoring visits), at the site close-out visit, and following drug reconciliation and documentation by the site monitor, all opened and unopened REGN9933 will be destroyed with Sponsor's approval or returned to the Sponsor or designee.

At specified time points during the study (eg, interim site monitoring visits), at the site close-out visit, and following drug reconciliation and documentation by the site monitor, all centrally sourced opened and unopened enoxaparin and apixaban will be destroyed with Sponsor's approval or returned to the Sponsor or designee

8.7.3. Treatment Accountability

All drug accountability records must be kept current.

The investigator must be able to account for all opened and unopened study drug. These records should contain the dates, quantity, and study medication

- dispensed to each participant
- returned from each participant (if applicable), and
- disposed of at the site or returned to the sponsor or designee.

All accountability records must be made available for inspection by the sponsor and regulatory agency inspectors; photocopies must be provided to the sponsor at the conclusion of the study.

8.7.4. Treatment Compliance

All drug compliance records must be kept current and made available for inspection by the sponsor and regulatory agency inspectors.

8.8. Concomitant Medications and Procedures

Any treatment administered from the time of informed consent to the final study visit will be considered concomitant medication. This includes medications that were started before the study and are ongoing during the study.

8.8.1. Prohibited Medications and Procedures

Administration of enoxaparin prior to TKA surgery is prohibited (Section 7.2.2 Exclusion criterion 10).

Anti-platelet therapy (except low doses of ASA ≤ 100 mg/day) is prohibited, unless indicated for treatment of an AE.

The following procedures/devices are prohibited after study drug has started:

- Use of spinal or epidural analgesia post-operatively
- Pneumatic compression devices

Subjects are prohibited from donating blood products through the EOS visit. Subjects are prohibited from donating sperm through the EOS visit. Subjects are prohibited from having planned, elective surgeries (except for TKA performed on day 1) through the EOS visit.

For patients assigned to the REGN9933 treatment arm, anticoagulant medications (including, but not limited to, vitamin K antagonists, heparins, DOACs) are prohibited after study drug has been started, unless they are indicated for treatment of an AE.

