8.8.2. Permitted Medications

Use of standard-of-care medications not listed as prohibited will be allowed.

For subjects assigned to either the enoxaparin or apixaban treatment arm, continued VTE prophylaxis (after completion of protocol-defined treatment, ie through the day of venography [or day 12, whichever is earlier]) is permitted, if deemed necessary by the site investigator based on local guidelines and/or clinical judgment. For the choice of agent to be used for subsequent VTE prophylaxis, it is preferred that the originally assigned treatment (ie enoxaparin or apixaban) is used. However, it is permissible to use other agents, as long as they are consistent with local regulations and standard of care for VTE prophylaxis after TKA surgery.

COVID-19 vaccination and any other vaccination can be administered as deemed necessary per the investigator based on his/her practice, standard of care, or as required based on mandatory vaccination programs. Vaccination is suggested to be administered preferably at least 1 week before the first dose of study drug (Section 7.2.2 Exclusion criterion 22), or at the earliest, 21 days following the last dose of study drug. Live-attenuated vaccines are generally not recommended during the study; however, use is allowed per the investigator's discretion.

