4.3. Prior / Concomitant Medication

Any treatment administered from the time of informed consent to the final study visit will be considered concomitant medication. This includes medications that were started before the study and are ongoing during the study.

Medications will be recorded from the day of informed consent until the end of study (EOS) visit. Medications will be coded to the anatomical therapeutic chemical (ATC) classification level 2 (therapeutic main group) and ATC level 4 (chemical/therapeutic subgroup), according to the latest available version of WHO Drug Dictionary (WHODD). Participants will be counted once in all ATC categories linked to the medication.

Prohibited concomitant medications/procedures

Administration of enoxaparin prior to TKA surgery is prohibited (see protocol Section 7.2.2 Exclusion criterion 10, and Section 8.8.1).

Anti-platelet therapy (except low doses of Acetylsalicylic acid (ASA) \leq 100 mg/day) is prohibited, unless indicated for treatment of an adverse event (AE).

The following procedures/devices are prohibited after study drug has started:

- Use of spinal or epidural analgesia post-operatively
- Pneumatic compression devices

Participants are prohibited from donating blood products through the EOS visit. Participants are prohibited from donating sperm through the EOS visit. Participants are prohibited from having planned, elective surgeries (except for TKA performed on day 1) through the EOS visit.

For participants assigned to the REGN9933 treatment arm, anticoagulant medications (including, but not limited to, vitamin K antagonists, heparins, DOACs) are prohibited after study drug has been started, unless they are indicated for treatment of an AE.

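### Section 8.8.1 bars anticoagulant prophylaxis as soon as REGN9933 has been started, with no exception for an infusion that is permanently stopped before the full dose

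*Protocol*

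**What the plan says.** Protocol 8.8.1 states that, in the REGN9933 arm, anticoagulants "are prohibited after study drug has been started, unless they are indicated for treatment of an AE". SAP 4.3 carries the same rule, opening with "For participants assigned to the REGN9933 treatment arm, anticoagulant medications". The trigger is the start of the drug, not a completed dose. Section 8.8.1 also bans pneumatic compression, in every arm and without exception: "The following procedures/devices are prohibited after study drug has started".

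The protocol expects that some infusions will not be finished. Section 8.4.1.2 says: "The infusion should be terminated and NOT restarted if any of the following AEs occur". Section 8.3.2 then covers people who stop: "Participants who permanently discontinue from study intervention (REGN9933, enoxaparin, or apixaban) should be encouraged to remain in the study". The subsection specific to REGN9933 takes another line: "As this is a single dose study of REGN9933, discontinuation of REGN9933 is not applicable". It continues: "Refer to Section 8.4 for the Management of Acute Reactions including interruption and termination of REGN9933 IV infusion".

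For the comparators, 8.3.2.2 and 8.3.2.3 say that VTE prophylaxis after a stop is for the investigator to decide. Section 8.8.2 permits prophylaxis after the treatment period in those arms only: "For subjects assigned to either the enoxaparin or apixaban treatment arm, continued VTE prophylaxis".

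Section 3.2.1 gives the reason for the REGN9933 ban: the drug keeps aPTT raised to at least day 35.

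**The concern.** The ban makes sense after a full 300 mg dose, because adding an anticoagulant to a long-acting one could cause bleeding. The rule does not distinguish that case from an infusion abandoned after a few minutes. Such a participant has just had a knee replacement, may have received little drug, cannot be given a changed REGN9933 dose (8.3.1) and is encouraged to stay in the study. Read literally, the text then denies them the anticoagulant prophylaxis that the investigator may choose for a comparator participant who stops.

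The same protocol says in 3.2.1 that a placebo arm would be inappropriate because approved prophylaxis exists. What is at stake is the care of one participant, not the trial's conclusion.

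**Working it through.** **1. The rules side by side**

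| Question | REGN9933 | Enoxaparin / apixaban |
|---|---|---|
| Can treatment be stopped permanently? | Yes (8.4.1.2, 8.3.2), though 8.3.2.1 says this does not apply | Yes (8.3.2.2, 8.3.2.3) |
| Who decides on VTE prophylaxis afterwards? | Not stated | The investigator |
| Anticoagulant ban after start of drug? | Yes, except to treat an AE (8.8.1, SAP 4.3) | None in 8.8.1 |
| Compression ban after start of drug? | Yes | Yes |

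**2. Does any sentence lift the anticoagulant ban?**

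- The AE exception covers treatment. Preventing a VTE that has not occurred is not treatment of an AE, and an anticoagulant does not treat anaphylaxis or a seizure.
- The clinical-judgment sentence in 8.4.1.1 concerns treating the reaction or stopping the infusion.
- The standard-of-care allowance in 8.8.2 excludes anything listed as prohibited, and anticoagulants are listed.
- Section 8.2.1 allows anticoagulation for a VTE that has already occurred.

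None of these closes the gap.

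**3. Dose delivered at an early stop**

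Table 1 gives 300 mg over 0.5 hour. At a constant rate (assumed), 300 mg / 30 min = 10 mg/min. A stop at 1, 3, 5 or 10 minutes delivers 10, 30, 50 or 100 mg. Section 3.2.2 reports sustained FXI inhibition in everyone treated at 100 mg or more, and describes the effect as dose-dependent over 3 to 300 mg. It does not say what happens to every individual below 100 mg, and it names no minimum effective dose. Figure 1, which plots the effect by dose, is not reproduced in the text used here. So neither the protection nor the duration of aPTT effect after a small dose can be judged.

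**4. How many participants**

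The documents give no termination rate. Section 1 reports no drug-related AEs in phase 1, with 5 cohorts × 6 = 30 people on REGN9933. The one-sided 95% upper limit for 0/30 is 1 − 0.05^(1/30) = 9.5%. For the 6 people at 300 mg it is 1 − 0.05^(1/6) = 39%. These data exclude little. With an assumed rate of 0.5–2%:

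- terminated at any time: 120 × 0.005 = 0.6 to 120 × 0.02 = 2.4
- terminated in the first 10 minutes, if stops are spread evenly over 30 minutes: one third of that, 0.2 to 0.8
- chance of at least one stop in the first 10 minutes: 1 − (1 − 0.00167)^120 = 18% to 1 − (1 − 0.00667)^120 = 55%

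**5. Size for one participant and for the trial**

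Section 1 puts VTE on placebo above 50%; 50% is used here for illustration. Section 11.2 assumes 22.4% on enoxaparin and 13% on REGN9933.

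- Avertable VTE risk: 0 if the partial dose still protects fully; 0.50 − 0.224 = 0.276, about 28 points, if it does nothing.
- Symptomatic part: below 0.276 × 0.15 = 0.041, about 4 points. This borrows the under-15% symptomatic share in 3.3.1, which comes from trials of FXI therapy against enoxaparin.
- Shift in the REGN9933 arm rate with no residual effect: n × (0.50 − 0.13)/120. For n = 0.2 to 0.8 this is 0.06 to 0.25 points. If all stops fall in the first 10 minutes (n = 0.6 to 2.4), it is 0.19 to 0.74 points. About three quarters of this (0.276/0.37 = 0.75) is due to the ban; the rest comes from the missed dose.
- For comparison, the planned difference is 22.4 − 13 = 9.4 points, and the standard error of a 13% rate in 120 people is √(0.13 × 0.87/120) = 3.1 points.

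**The case against.** The best reply is that the situation is rare and not a trap. Exclusions 8 and 17 remove people with hypersensitivity to study treatments, severe or multiple allergies, or earlier anaphylaxis. Section 3.3.1 cites proximal DVT in only 13% of placebo patients. An investigator could give prophylaxis and record a deviation, and 13.4 allows an urgent change ahead of ethics approval to remove an immediate hazard. ASA up to 100 mg/day, symptom checks and the day 10 venogram also remain.

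All of this is true and limits the size of the point. It does not supply the missing rule. Withdrawal also has a price: the early termination visit in 9.1.2 uses the End of Study assessments, which do not include venography in Table 2.

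A reader might infer several stronger things that the documents do not support:

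- *The participant must leave the study to get prophylaxis.* Nothing makes use of a prohibited medication a mandatory reason for withdrawal.
- *The participant is effectively on placebo.* The effect of small doses cannot be judged from the text.
- *100 mg marks the dose below which the ban loses its reason.* It is not presented as an effective-dose threshold, and the text gives no day-35 aPTT result for it.
- *The compression ban is a further disadvantage of the REGN9933 arm.* It applies to all arms, and whether the discretion in 8.3.2.2 and 8.3.2.3 overrides it is unclear.
- *The figures above are upper bounds.* They rest on an assumed termination rate and on exactly 50% where the protocol says more than 50%.

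**Conclusion.** The gap in the text is real. Followed as written, the protocol denies anticoagulant prophylaxis to a REGN9933 participant whose infusion is stopped early, unless there is a deviation or a withdrawal, while comparator participants who stop are covered by investigator discretion. The reason given for the ban is not shown to extend to a small delivered dose.

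The point is narrow. Under the assumed 0.5–2% termination rate, 0.6 to 2.4 infusions of 120 would be terminated, and 0.2 to 0.8 in the first ten minutes if stops are evenly spread. The consequence for one such person ranges from nothing to roughly 28 points of mostly asymptomatic VTE risk, or somewhat more if untreated risk is well above 50%. The effect on the primary result is negligible against a 3.1-point standard error. The case for a change rests on individual safety, on the contrast with the comparator arms and on the low cost, not on these illustrative figures.

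**What to change.** Add to Protocol 8.3.2.1: *If the REGN9933 infusion is permanently terminated before completion, the investigator decides on further VTE prophylaxis, taking into account the dose received and the bleeding risk.* Add the matching exception to the anticoagulant ban in 8.8.1 and copy it to SAP 4.3. If an exception to the compression ban is made as well, extend it to participants in any arm who permanently stop study drug; a comparator participant stopped for bleeding may need a non-drug method most.

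Set no 100 mg cut-off, since the text does not support one. Keep the mITT analysis as randomised.

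The cost is a sentence and an exception clause, repeated in the SAP, with no extra visits or participants and no analysis change. The downside is possible additive bleeding from a partial dose plus an anticoagulant. That is why the wording asks the investigator to weigh dose and bleeding risk rather than making prophylaxis automatic.

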8.8.2. Permitted Medications

Use of standard-of-care medications not listed as prohibited will be allowed.

For subjects assigned to either the enoxaparin or apixaban treatment arm, continued VTE prophylaxis (after completion of protocol-defined treatment, ie through the day of venography [or day 12, whichever is earlier]) is permitted, if deemed necessary by the site investigator based on local guidelines and/or clinical judgment. For the choice of agent to be used for subsequent VTE prophylaxis, it is preferred that the originally assigned treatment (ie enoxaparin or apixaban) is used. However, it is permissible to use other agents, as long as they are consistent with local regulations and standard of care for VTE prophylaxis after TKA surgery.

COVID-19 vaccination and any other vaccination can be administered as deemed necessary per the investigator based on his/her practice, standard of care, or as required based on mandatory vaccination programs. Vaccination is suggested to be administered preferably at least 1 week before the first dose of study drug (Section 7.2.2 Exclusion criterion 22), or at the earliest, 21 days following the last dose of study drug. Live-attenuated vaccines are generally not recommended during the study; however, use is allowed per the investigator's discretion.

9. STUDY SCHEDULE OF EVENTS AND PROCEDURES

9.1. Schedule of Events

In light of the public health emergency related to COVID-19, the continuity of clinical study conduct, and oversight may require implementation of temporary or alternative mechanisms. Examples of such mechanisms may include, but are not limited to, any of the following: phone contact, virtual visits, telemedicine visits, online meetings, non-invasive remote monitoring devices, use of local clinic or laboratory locations, and home visits by skilled staff. Additionally, no waivers to deviate from protocol enrollment criteria due to COVID-19 will be granted. All temporary mechanisms utilized, and deviations from planned study procedures are to be documented as being related to COVID-19 and will remain in effect only for the duration of the public health emergency.

Study assessments and procedures are presented by study period and visit in [Table 2](#).

Definitions

For safety variables, 3 observation periods are defined:

- Screening period - the time from signing the ICF to before the first dose of study drug.
- On-treatment period - the day from first dose of study drug to the date of day 12.
- Follow-up period - the end of the on-treatment period to EOS visit.

Table 2: Schedule of Events

Study Procedure	Screening	On-treatment			Follow-up	
	Visit 1	Baseline Visit 2	Visit ^{1,2} 3	Visit ¹ 4	Visit 5	End of Study/ Visit 6
Day	-30 to -1	1	5	10	30	75
Window (day)			±1	±2	±3	±5
Screening/Baseline:						
Inclusion/Exclusion	X					
Informed consent	X					
Informed consent for pharmacogenomics research (optional)	X					
Informed consent for future biomedical research (optional)	X					
Medical History	X					
Demographics	X					
FSH ³	X					
GFR (MDRD)	X					
Urine drug screen	X					
Randomization		X ⁴				
Treatment:						
TKA		X				
Administer REGN9933		X ⁵				
Administer enoxaparin			X ⁶			
Administer apixaban			X ⁶			
Patient diary (for self-administration of apixaban/enoxaparin)			X			
Efficacy:						
Venography of the operated leg				X		
Assessment for symptomatic VTE ⁷		X	X	X	X	X
Safety:						
Height	X					
Weight	X					

Study Procedure	Screening	On-treatment			Follow-up	
	Visit 1	Baseline Visit 2	Visit ^{1,2} 3	Visit ¹ 4	Visit 5	End of Study/ Visit 6
Vital Signs	X	X	X	X	X	X
Physical examination	X	X				X
Electrocardiogram	X					
Assessment for surgical site bleeding		X	X	X		
Assessment for bleeding events		X	X	X	X	X
Adverse events	X	X	X	X	X	X
Concomitant medications and treatment	X	X	X	X	X	X
Laboratory Testing						
Hematology	X	X ⁸		X		X
Blood chemistry	X	X ⁸		X		X
Coagulation panel	X	X ⁸		X		X
Urinalysis	X					X
Pharmacokinetics and Immunogenicity Sampling						
Drug concentration sample (REGN9933)		X ⁸	X	X	X	X
ADA (REGN9933)		X ⁹				X
Plasma for total FXI concentration		X ⁸	X	X	X	X
Biomarkers						
Plasma for aPTT, PT (central lab)		X ⁸	X	X	X	X
Plasma for FXI activity (FXI:C) and TGA		X ⁸	X	X	X	X
Serum for exploratory research		X ⁸	X		X	X
Plasma for exploratory research		X ⁸	X		X	X
Optional Pharmacogenomics samples						
Whole blood sample for RNA isolation (optional) ¹⁰		X				X
Whole blood sample for DNA isolation (optional) ¹⁰		X ¹¹				

ADA: anti-drug antibody; aPTT: activated partial thrombin time; GFR: glomerular filtration rate; FSH: follicle-stimulating hormone; FXI: Factor XI; FXI:C: Factor XI functional activity; MDRD: Modification of Diet in Renal Disease; PT: prothrombin time; TGA: thrombin generation assay; TKA: total knee arthroplasty; VTE: venous thromboembolism

Table 3: Schedule of Events: Visit 2 Blood Collection

Baseline Visit 2 (Day 1)			
Study Procedure	Pre-operatively	Post-operatively	
		Pre-dosing Up to 1 hour prior to dosing	Post-dosing REGN9933 only: as close as possible to 1 hour post-dose
Laboratory Testing			
Hematology	X ¹		
Blood chemistry	X ¹		
Coagulation panel	X ¹		
Urinalysis			
Pharmacokinetics and Immunogenicity Sampling			
Drug concentration sample (REGN9933)		X ²	X ²
ADA (REGN9933)		X ²	
Plasma for total FXI concentration	X ¹	X ³	X ²
Biomarkers			
Plasma for aPTT, PT (central lab)	X ¹	X ³	X ²
Plasma for FXI activity (FXI:C) and TGA	X ¹	X ³	X ²
Serum for exploratory research	X ¹	X ³	
Plasma for exploratory research	X ¹	X ³	

ADA: anti-drug antibody; aPTT: activated partial thrombin time; FXI: Factor XI; FXI:C: Factor XI functional activity; PT: prothrombin time; TGA: thrombin generation assay

